### 6.3.2. Neurological Outcome

Neurologic function as assessed by the NIHSS is an exploratory endpoint. Actual values at scheduled visits will be summarized descriptively.

### 6.3.3. Pharmacokinetics

PF-05230907 concentration in plasma is an exploratory endpoint. There will be  $C_{5\text{min}}$  and  $C_{45\text{min}}$  denoting the plasma concentration at 5 minutes and 45 minutes post-dose, respectively. *Available plasma concentration of PF-05230907 will be descriptively summarized and plotted by nominal PK sampling time and dose group. Due to the short half-life ( $t_{1/2}$ ) and limited sampling, noncompartmental parameters will not be calculated for the study report.*

Presentation of pharmacokinetic data will include:

- Descriptive statistics (n, mean, SD, %CV, median, minimum, maximum) of plasma concentrations will be presented in tabular form by dose group and nominal time.
- Dose-normalized  $C_{5\text{min}}$  and  $C_{45\text{min}}$  will be summarized using data pooled across dose groups in which different PF-05230907 doses were administered.

As data permit, pharmacokinetic data from this study may be analyzed using modeling approaches and may also be pooled with data from other studies to investigate any association between PF-05230907 exposure and biomarkers or significant safety/efficacy endpoints. The results of these analyses, if performed, may be reported separately.

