### **3.3.3. Pharmacokinetics**

*PF-05230907 concentration in plasma* is an exploratory endpoint. Blood samples will be collected at screening, 5 minutes and 45 minutes post-dose for this evaluation. *Samples obtained within 10% of the nominal time (eg, within 6 minutes of a 60 minute sample) from dosing or  $\pm 2$  minute for samples less than 10 minutes from dosing will not be captured as a protocol deviation.*

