#### **4.4. Protocol Deviations**

A full list of protocol deviations will be compiled and reviewed by clinician, clinical pharmacologist, and statistician to identify major and minor deviations prior to database release. Different protocol deviations may have impact on different analysis populations. At the discretion of the clinician, clinical pharmacologist, and statistician, major violators might be excluded from impacted analysis populations. The decision and rationale for exclusion will be documented. According to the protocol, any deviations from the PK/PD, immunogenicity processing steps, including any actions taken, must be documented and reported to the sponsor. *On a case-by-case basis, the sponsor may make a determination as to whether sample integrity has been compromised. Any sample deemed outside of established stability, or of questionable integrity, will be considered a protocol deviation.*

If dosing error is greater than 20%, then the subject may be excluded from the group statistics of the PK and/or PD analysis when deemed appropriate.

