#### **5.4.2. Pharmacokinetic Concentrations and Parameters**

##### **5.4.2.1. PF-05230907 Concentrations Below the Limit of Quantification**

In all data presentations except listings, PF-05230907 concentrations assayed as below the limit of quantification (BLQ) will be set to zero. In listings BLQ values will be reported as “<LLQ”, where LLQ will be replaced with the value for the lower limit of quantification.

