##### **5.4.2.2. Deviations, Missing Concentrations and Anomalous Values**

In summary tables and plots of median profiles, concentrations will be set to missing if at least one of the following cases is true:

1. A concentration has been collected as ND (Not Done) or NS (no sample).
2. A deviation in sampling time is of sufficient concern or a concentration has been flagged anomalous by the pharmacokineticist.

Summary statistics will not be presented at a particular time point if more than 50% of the data are missing.

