#### **5.4.5. Extended Time Post Dose Visit Window**

The Schedule of Activities table in the study protocol defined the visit window and the study activities should take place within these visit windows. However, some activities such as laboratory testing, might occur out of the protocol specified visit window in reality. For the purpose of statistical analysis, Table 4 defines extended visit windows. If the deviation is determined not to compromise scientific integrity of the assessment upon review, and the result is obtained within the New Study Specified Visit Window for Statistical Analysis, then the result will be included in the analysis to minimize missing data issue.

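### PK is summarised at nominal times, with dose-normalised C5min and C45min pooled, for a drug with a 3.7–4.6 min half-life; the only analysis limits in minutes (1–9 and 15–75) are too wide for it

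*SAP*

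**What the plan says.** SAP 6.3.3 says that available concentrations "will be descriptively summarized and plotted by nominal PK sampling time and dose group", with mean, SD, %CV, median, minimum and maximum. Dose-normalised C5min and C45min "will be summarized using data pooled across dose groups in which different PF-05230907 doses were administered". Actual elapsed time does not appear in these summaries. Protocol 7.4 makes the recording of the exact sample time a condition of its tolerance, so the times should exist.

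The timing rules for the two post-dose PK draws are spread over several places:

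- **Deviation capture** (Protocol 7.4, SAP 3.3.3). "Samples obtained within 10% of the nominal time", or within 2 minutes for draws under 10 minutes, are not captured as protocol deviations.
- **Visit window** (Schedule of Activities; Protocol 6.2.2 and 6.2.3). ±2 min at 5 min and ±15 min at 45 min.
- **Analysis window** (SAP 5.4.5 and Table 4). ±4 min at 5 min and ±30 min at 45 min. An out-of-window result enters only if it lies inside Table 4 and also passes a review: "If the deviation is determined not to compromise scientific integrity of the assessment upon review".
- **PK-specific exclusion** (SAP 5.4.2.2). A concentration is set to missing if "A deviation in sampling time is of sufficient concern or a concentration has been flagged anomalous by the pharmacokineticist".
- **Deviation review** (SAP 4.4). "A full list of protocol deviations will be compiled and reviewed by clinician, clinical pharmacologist, and statistician to identify major and minor deviations". Major violators might then be excluded. For dose there is a number: "If dosing error is greater than 20%, then the subject may be excluded from the group statistics of the PK and/or PD analysis".

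Concentrations "assayed as below the limit of quantification (BLQ) will be set to zero" in everything except listings (SAP 5.4.2.1).

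**The concern.** With a half-life of about four minutes, a few minutes' difference in sampling time changes the concentration materially. A summary labelled C45min that mixes draws taken well apart describes the sampling clock as well as exposure. Dose normalisation does not remove this, and pooling across doses leaves no dose contrast against which a reader could notice it.

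The rules do not settle which draws count. A sample at 33 min is on schedule under Protocol 6.2.3, is by implication a captured deviation under Protocol 7.4, and is never reached by SAP 5.4.5, which deals only with results outside the protocol window. Whether it enters C45min then depends on judgement under SAP 4.4 or 5.4.2.2, neither of which gives a time threshold.

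At stake is the exposure summary in the study report. C5min is the only scheduled near-peak concentration in patients, and SAP 7.4.2 intended PK summaries to help place clinical exposure relative to the NOAEL.

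**Working it through.** **Inputs.** Half-life 4.6 min at 3 µg/kg and 3.7 min at 5 µg/kg; peak at 2–5 min; non-detectable by 40 min in all subjects but one, who was in the 5 µg/kg group (all Protocol 1.3.2). Windows as listed above. Dose grid from Protocol Table 2.

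**1. The plan's windows reproduce.** Table 4: 5 ± 4 = 1–9 min and 45 ± 30 = 15–75 min, as printed. Protocol: 5 ± 2 = 3–7 min and 45 ± 15 = 30–60 min. The 10% rule: 0.10 × 45 = 4.5, so 40.5–49.5 min.

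**2. Effect of timing alone.** For mono-exponential decline at a fixed dose, the ratio between two draws Δt minutes apart is 2^(Δt / half-life).

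| Comparison | Δt (min) | half-life 4.6 | half-life 3.7 |
|---|---|---|---|
| 45-min draw, 10% rule: 40.5 vs 49.5 | 9 | 3.88 | 5.40 |
| 45-min draw, protocol window: 30 vs 60 | 30 | 91.9 | 275.9 |
| 5-min draw, protocol window: 5 vs 7 | 2 | 1.35 | 1.45 |
| 5-min draw, Table 4: 5 vs 9 | 4 | 1.83 | 2.12 |

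Only the late side is computed for the 5-min draw. Draws at 1–4 min may precede the peak, where this formula does not apply.

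**3. Scale against dose.** From 5 µg/kg upward, one grid step is a factor of 1.20–1.33 and two steps 1.50–1.67. A 7-min draw therefore shifts the value by more than one dose level, and a 9-min draw by more than two. From the starting dose to the top of the grid is 47 / 5 = 9.4 fold, smaller than the 92–276 fold that the ±15 min window allows. This is the planned grid; the documents do not give the doses reached.

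**4. Scale against the plan's own dose-error figure.** A concentration change of +20% corresponds to log2(1.2) × half-life = 1.21 or 0.97 min. A change of −20% corresponds to log2(1.25) × half-life = 1.48 or 1.19 min. So a timing error of about 1.0–1.5 min moves the concentration as much as the 20% dose error that SAP 4.4 names.

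**5. How much of the 45-min range would be seen.** Under dose linearity, an on-time 45-min level at 10 µg/kg relative to a 40-min level at 5 µg/kg is 2 × 2^(−5 / half-life) = 0.94 or 0.78. The 40-min level was non-detectable in all but one subject. On-time 45-min values at doses up to 10 µg/kg are therefore probably below quantification and set to zero. The quantification limit is not given, so this cannot be made firm. SAP 5.4.2.2 suppresses statistics when more than 50% of data are missing, but its missing-value cases do not include values set to zero, so a mostly-zero C45min could still be tabulated.

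**The case against.** The other side has five points.

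*There are safeguards.* SAP 5.4.2.2 is written for PK and lets the pharmacokineticist remove a mistimed or anomalous value, and SAP 4.4 brings in a clinical pharmacologist. This stands in part: the most extreme draws would probably be caught. What it does not supply is a threshold for the intermediate ones.

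*A limit in minutes exists.* A reader might infer that no rule gives one. That is not so: SAP 5.4.5 requires both passing review and falling inside Table 4. The sound criticism is that these limits are too wide for this half-life, and that the other two reviews have none.

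*Table 4 does not name PK.* True; SAP 5.4.5 gives laboratory testing as its example. But Table 4 covers the two visits at which post-dose PK is drawn and excludes nothing, so its application to PK is left open. The protocol's own ±15 min window raises the problem without it.

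*The fold ranges are worst cases.* This stands. Protocol 7.4 asks for every effort to sample at the exact time, and no spread of actual times is reported. A reader might also infer that one early draw would multiply the pooled C45min mean by some large factor. The documents do not support such a figure: it needs quantifiable on-time values, which step 5 makes doubtful, and no exclusion under SAP 5.4.2.2.

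*The summary follows the protocol, and little hangs on it.* Protocol 9.5.1 specifies nominal-time description and declines noncompartmental parameters because of the short half-life and limited sampling. SAP 6.3.3 also reports medians, which a single outlier barely moves, and permits modelling. All true, and it keeps the point small. The reason for declining those parameters applies equally to a pooled nominal-time C45min.

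**Conclusion.** The point holds and is minor. Summarising and pooling by nominal time, when actual times are recorded and the half-life is 3.7–4.6 min, is a weaker choice than the data allow. The three 45-min tolerances serve different purposes (deviation capture, visit window, analysis window), but nothing says which governs the PK summary.

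The sizes in the table rest on healthy-volunteer half-lives carrying over to patients, mono-exponential decline out to 60 min, timing as the only source of variation, quantifiable values, and no exclusion on review. They are what the rules permit, not what happened. If all 45-min draws fell within 40.5–49.5 min, the range would be 3.9–5.4 fold at most.

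A reader might infer that dose decisions were exposed to this. They were not: PK does not enter the mCRM, and SAP 7.4.2 says PK and PD data are not required to proceed to the next cohort. SAP Section 1 records that the study was stopped after 21 subjects. The effect is confined to an exploratory exposure summary. Nor do the documents show a corresponding defect in the aPTT and AUEC analyses of SAP 6.2.1, which do not specify nominal times.

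**What to change.** In the SAP:

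- Plot and list PK concentrations against actual elapsed time from dosing (SAP 6.3.3).
- State in SAP 5.4.5 that Table 4 does not apply to PK samples.
- Restrict nominal-time and dose-normalised C5min to draws within ±2 min.
- For the 45-min draw, list individual values with actual times and give the number below quantification. Alternatively, limit any C45min summary to draws within the 10% tolerance already in Protocol 7.4 and SAP 3.3.3.
- Reconcile the three 45-min tolerances (10%, ±15 min, ±30 min) by saying which one governs PK analysis.

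The cost is a few sentences and a small programming change, since exact times are already collected. Protocol Section 9 lets the SAP modify the planned analyses, and PK is not a primary endpoint. The downside is that a few more PK values will be missing from the nominal-time tables; they would still appear in the actual-time plots and listings.

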### **6.3.4. Exploratory Biomarkers**

#### **6.3.4.1. Pharmacodynamic Biomarkers**

*Change in other exploratory biomarkers that may reflect pharmacologic effect of PF-05230907 or ICH progression may be evaluated.*

For aPTT or PTT, results obtained through Day 4 will be included in the analyses described in Section 6.2.1 to evaluate the changes from baseline. For other exploratory biomarkers available, they will be analyzed in the same manner as described in Section 6.2.1.

#### **6.3.4.2. Neuro-inflammation Biomarkers**

Exploratory endpoint includes *potential biomarkers of neuro-inflammation and/or neurological outcomes to better understand ICH and/or its outcomes.*

Listing of available neuro-inflammation biomarker data will be generated.

### **6.3.5. Immunogenicity**

Immunogenicity analysis will be conducted on the immunogenicity analysis set as defined in Section 4.3.3. Listing of baseline values and changes from baseline to Day 43 in Anti-CHO protein antibodies and anti- PACE furin antibodies will be generated. A summary of positive anti-CHO or anti-PACE furin antibody immune responses may be generated when applicable.

### **6.3.6. Health Resource utilization**

Duration of stay in ICU unit, general ward (medical/surgical unit), main hospital stay including ICU/general ward, inpatient rehabilitation center, and other hospital units will be displayed in listings. The duration of stay for each type of hospital unit or outpatient rehabilitation center will be derived according to Section 5.3.3.4.

## **6.4. Subset Analyses**

Not applicable.

## **6.5. Baseline and Other Summaries and Analyses**

### **6.5.1. Baseline Summaries**

The following analyses will be based on the FAS overall and separately by dose group.

### 6.5.1.1. Demographic Characteristics

Demographic characteristics and physical measurements will be summarized descriptively.

- Age (years): summary statistics; Age categories : <65 years,  $\geq$ 65 years
- Sex: Male, Female
- Race: White, Black, Asian, Other
- Ethnic origin: Hispanic/Latino (Yes/No)
- Physical measurements include weight (kg), height (cm), and Body Mass Index (BMI) ( $\text{kg}/\text{m}^2$ )

Site codes will be used for the determination of the subject's geographic region.

The listing of demographics and baseline characteristics by dose group will include the following information: subject ID, dose group, age, sex, race, ethnicity, height (cm), weight (kg), and BMI ( $\text{kg}/\text{m}^2$ ).

### 6.5.1.2. Medical History and Smoking History

Medical history will be summarized descriptively from the 'Significant Medical History' eCRF page. In addition, medical history will be coded using the most current available version of Medical Dictionary for Regulatory Activities (MedDRA) and MedDRA preferred term as event category and MedDRA primary system organ class (SOC) as summary category. Each subject will be counted only once within each SOC or preferred term. It will be displayed in terms of frequency tables ordered by primary SOC and preferred term in alphabetical order.

Smoking history will be summarized by the classification: Smoker, Ex-Smoker, and Never Smoked.

Listings of the medical history and smoking history by dose group will be generated.

### 6.5.1.3. Intracerebral Hemorrhage Characteristics

Intracerebral Hemorrhage (ICH) baseline information including date of ICH onset, time of ICH onset, time since ICH onset to study drug start, date of ICH evaluation including risk factors, ICH volume at baseline CT scan (mL) by ABC/2 assessment and by central vendor analysis, and vascular malformation ruled out (Yes/No) will be summarized descriptively. Listing of the relevant information collected from the "Primary Diagnosis", "Dosing Record", and "Intracerebral Hemorrhage Details" eCRF pages will be generated by dose group. Refer to Section 5.3.3.2 for the derivation of the time since ICH onset to study drug

start. Analysis results obtained from central vendor will also be summarized and included in the description of baseline ICH characteristics.

### **6.5.2. Study Conduct and Subject Disposition**

The following analyses will be performed based on the FAS overall and separately by dose group.

#### **6.5.2.1. Subject Disposition**

Summary of subject disposition by dose group will be provided. The percentages will be calculated based on the number of subjects in the FAS where appropriate.

- Total number of subjects screened overall
- Number of subjects assigned to study treatment
- Number of subjects who completed the study
- Number and percentage of subjects who withdrawn from the study overall and by primary reason for withdrawal
- Number and percentage of subjects who entered outpatient follow-up

In addition, the number and percentage of treated subjects by center will be summarized.

#### **6.5.2.2. Protocol Deviations**

All protocol violations that impact the subject safety, the conduct of the study, and/or the study evaluation will be reported. These include

- Subjects who are dosed on the study even though they did not strictly meet the inclusion/exclusion criteria
- Subjects who receive an incorrect dose
- Deviations from Good Clinical Practice (GCP), and/or the conduct of the study

The identification of these and other CSR-reportable deviations will be based on the inclusion/exclusion criteria and other criteria presented in the protocol. Refer to Section 4.4 for details.

#### **6.5.3. Study Treatment Exposure**

Analyses of exposure to study drug will be based on the safety analysis set by dose group assigned at enrollment. The duration of study drug administration will be summarized and included in the listing of study drug administration based on the information collected from the “Dosing Record” eCRF form.

The summary of study treatment exposure and compliance will include the following information:

- Treatment duration (minutes)
- Concentration (ng/mL)
- Actual dose administered ( $\mu$ g)
- Actual dose administered/ Baseline weight ( $\mu$ g/kg)

Sensitivity analyses will be conducted to assess the robustness of study conclusion based on the actual dose administered. For weight-based dosing evaluation, the weight-adjusted dose is calculated as the actual dose administered/baseline weight ( $\mu$ g/kg). The last available weight of the subject measured on or prior to the day of dosing will be used. If actual weight cannot be obtained prior to dosing, the earliest post-dose directly measured weight will be used for the evaluation. For flat dose evaluation, the treatment dose level is the actual dose administered in  $\mu$ g.

Refer to Section 6.3.3 for PK analysis of the drug concentration.

#### 6.5.4. Concomitant Medications and Non-Drug Treatments

The analyses will be based on the safety analysis set overall and by dose group.

*Concomitant treatments and medications taken within 7 days prior to study enrollment will be documented as prior treatments and medications. Treatments and medications taken after Day 1 Hour 0 (post-dose administration) will be documented as concomitant treatments and medications.* All concomitant treatments and medications taken during the study will be reported with the indication and start and stop dates of administration.

Listings of prior treatments and medications, concomitant medications and treatments will be created from the information collected on the 'Previous and Concomitant Drug Treatment' eCRF page. The concomitant drug start and stop day relative to the date of PF-05230907 administration will be shown.

Summary of prior and concomitant medications will include the number and percentage of subjects by Anatomical Therapeutic Chemical (ATC) Classification levels and preferred term. A subject will be counted only once within a given drug class and within a given drug name, even if he or she received the same medication at different times. If any prior or concomitant medication is classified into multiple ATC classes, the medication will be summarized separately under each of these ATC classes. The summary tables will be sorted on decreasing frequency of drug class and decreasing frequency of drug name in a given drug class. In case of equal frequency regarding drug class (respectively drug name), alphabetical order will be used. In case any specific medication does not have ATC classification level coded term, it will be summarized under 'Unavailable ATC classification' category.

All prior and current non-drug treatment and/or procedures will be summarized according to the 'Previous and Current Non-Drug Treatment/Procedure' eCRF page. Number and

percentage of subjects with concurrent non-drug treatment/procedure will be tabulated overall, by dose group, and by reason for non-drug treatment/procedure. Listing of previous and current non-drug treatment/procedure will be generated with start day and stop day relative to the date of PF-05230907 administration.

## 6.6. Safety Summaries and Analyses

Safety analyses will be conducted based on the safety analysis set. All safety endpoints as described in Section 3 will be summarized descriptively in tabular and/or graphical format and listed, where appropriate, in accordance with Pfizer data standards. Details of the analyses are described in the following sections.

### 6.6.1. Adverse Events

Treatment emergent TIEs through Day 8, treatment emergent adverse events (TEAEs) through Day 8, and treatment emergent SAEs through Day 43 are primary endpoints. Any adverse events occurring following the start of treatment or increasing in severity during the observation period will be counted as treatment emergent. In addition, three categories of interest through Day 91 are defined as follows:

- **Related Adverse Events:** adverse events with relationship or unknown relationship to study treatment reported by the investigator and recorded on the AE eCRF page with CAUSALITY = YES/UNKNOWN or missing
- **Adverse Events Leading to Permanent Treatment Discontinuation or withdrawal from study:** adverse events leading to permanent discontinuation of study treatment or withdrawal from study as recorded on the AE eCRF page, Action taken with study treatment dose = Permanently discontinued or subject withdrawn from study
- **Adverse Events with severity Grade 3 or higher:** adverse events of Grade 3 to Grade 5 as recorded on the AE eCRF page

The corresponding AE listings will include all AEs (whether treatment emergent or not), study day, and the relevant information collected from the AE eCRF pages for the primary endpoints, and the categories of interest aforementioned. The incidence of AEs that fall within the respectively reporting period will be summarized and listed by body system, severity and causality by dose group. AEs outside the period considered will be flagged in the listings.

Adverse events will be summarized by worst severity per subject, using the latest version of MedDRA preferred term as event category and MedDRA primary system organ class (SOC) body term as Body System category. The number and percentage of subjects with the AE in each categories of interest will be summarized overall and by dose group, by

primary SOC and preferred term in decreasing frequency observed in all dose groups combined.

Each subject will be counted only once within each SOC or preferred term. If a subject experiences more than one AE within a SOC or preferred term for the same summary period, only the AE with the strongest relationship or the worst severity, as appropriate, will be included in the summaries of relationship and severity.

In case a subject has events with missing and non-missing grades, the maximum of the non-missing grades will be displayed. No imputation of missing grades will be performed.

